APPENDIX 2: COMPOSITE RESPONSE CRITERIA FOR PATIENTS WITH LOCALLY ADVANCED CSCC

These criteria are designed primarily for patients whose target lesions will be evaluated by clinical measurements (ie caliper or ruler measurements). This appendix also provides composite response criteria for disease that is measurable by both clinical response criteria and radiographic images. These patients will be followed by clinical measurements and will also undergo radiologic imaging at baseline, and this will also be performed serially at each response assessment unless the investigator deems that baseline radiologic imaging was uninformative. Radiologic imaging will be essential in the evaluation of tumors that have subdermal components that cannot be adequately assessed by clinical measurements.

A new cutaneous lesion consistent with CSCC will be considered as PD if the lesion is ≥ 10 mm in both maximal perpendicular diameters, and can be clearly documented as not being previously present, unless it is confirmed on biopsy not to be consistent with CSCC. If a new cutaneous lesion is not biopsied or if the histology is inconclusive, it should be considered CSCC and deemed PD.

Composite Response Criteria

These criteria are for patients who have locally advanced or metastatic CSCC that is measurable by BOTH clinical response criteria by clinical measurement and radiologic imaging.

Clinical Response (caliper/ ruler)	Radiographic Response (CT/MRI)	Composite (Overall) Response
CR	CR or NA ^a	CR
NA ^a	CR	CR
CR	PR or SD	PR
PR	CR, PR, SD or NA ^a	PR
NA	PR	PR
SD	CR or PR	PR
SD	SD or NA ^a	SD
NA ^a	SD	SD
PD	Any	PD
Any	PD	PD

^a NA indicates “Not applicable” (eg, because the assessment was not done)

In addition, if all previously inoperable target lesions are rendered operable with clear margins obtained at the time of surgery, this will be considered a PR.

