5 STUDY ENROLLMENT AND WITHDRAWAL

5.1 PARTICIPANT INCLUSION CRITERIA

1. Histologically confirmed diagnosis of invasive CSCC.

Notes: Patients with mixed histologies (eg, sarcomatoid, adenosquamous) generally will not be eligible. Patients with mixed histology in which the predominant histology is invasive CSCC (with only a minimal component of mixed histology) may be eligible, after communication with

and approval from the each site principal investigator.

2. Immunocompromised patients with invasive CSCC. Immunocompromised patients are defined as:
 - a. History of HIV with CD4 counts ≥ 200 and no AIDS-defining illnesses.
 - b. History of treated or active hematologic malignancies including lymphoma, Hodgkin's disease, chronic lymphocytic leukemia, chronic myeloid leukemia, multiple myeloma, and myeloproliferative neoplasm.
3. At least 1 lesion that is measurable by study criteria by RECIST 1.1. Externally visible cutaneous SCC target lesion(s) greater than >10 mm, bi-dimensional measurements of the external lesion(s) with a color photograph may be used as target lesions.
4. Eastern Cooperative Oncology Group (ECOG) performance status 0-2.
5. ≥ 18 years old.
6. Hepatic function:
 - a. Total bilirubin $\leq 3.0 \times$ upper limit of normal (ULN)
 - b. Transaminases $\leq 5.0 \times$ ULN
 - c. Alkaline phosphatase (ALP) $\leq 5.0 \times$ ULN
7. Renal function: Estimated creatinine clearance (CrCl) >30 mL/min.
8. Bone marrow function:
 - a. Hemoglobin ≥ 8.0 g/dL
 - b. Absolute neutrophil count (ANC) $\geq 1.0 \times 10^9/L$
 - c. Platelet count $\geq 50 \times 10^9/L$
9. Ability to provide signed informed consent.
10. Ability and willingness to comply with scheduled visits, treatment plans, laboratory tests, and other study-related procedure.
11. Anticipated life expectancy >12 weeks.
12. CSCC not amenable to surgery or radiation therapy such as unresectable tumors determined by surgeons, surgical morbidity unacceptable by the patients, inability to deliver radiation safely determined by radiation oncologists, or radiation related toxicities unacceptable by the patients.

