7.4 CONCOMITANT MEDICATIONS, TREATMENTS, AND PROCEDURES

All concomitant prescription medications taken during study participation will be recorded on the case report forms (CRFs).

All additional local therapies for metastatic lesions (including, but not limited to EBRT, surgery, embolization, ethanol injections, etc.) will be recorded on CRFs.

- Steroid: Treatment with oral/IV corticosteroids (>10mg daily prednisone equivalent) is not allowed for non-immunological toxicities. Treatment with oral/IV corticosteroids (>10mg daily prednisone equivalent) for immunological toxicities is permitted as detailed in the dose modification sections.
- Use of corticosteroids (\leq 10 mg daily prednisone equivalents) is allowed. Inhaled or topical steroids and adrenal replacement doses $>$ 10 mg daily prednisone equivalents are permitted in the absence of active autoimmune disease.
- Palliative radiation therapy is allowed to non-target lesions at the discretion of the treating physician. As concurrent radiotherapy and Cemiplimab-rwlc have not been formally evaluated, in cases where palliative radiotherapy is required for a tumor lesion, then Cemiplimab-rwlc should be withheld for at least 1 week before, during, and 1 week after radiation. Subjects should be closely monitored for any potential toxicity during and after receiving radiotherapy.
- Surgical resection of new and non-target cutaneous lesions that are $<$ 10mm is allowed at the discretion of the treating physician. Surgical resection of target lesions is only permissible if all previously identified target lesions are rendered operable. For guidance on the impact on response assessment refer to the composite response criteria found in Appendix 2.

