10.4.2 ANALYSIS OF THE PRIMARY EFFICACY ENDPOINT(S)

The primary endpoint for efficacy analyses is the ORR. All response assessments are done by RECIST 1.1 analysis of radiologic scans. In some patients, response assessments include photos and radiologic scans and evaluated by composite efficacy criteria (see Appendix 2). Clinical lesions will only be considered measurable when they are superficial (eg, skin nodules and palpable lymph nodes) and ≥ 10 mm (≥ 1 cm) diameter as assessed using calipers (e.g., skin nodules). In the case of skin lesions, documentation by color photography, including a ruler to estimate the size of the lesion, is recommended. Patients who are deemed as not evaluable according to RECIST 1.1 or inevaluable by the composite efficacy criteria will be considered as not reaching PR/CR for ORR.

We expect to complete the accrual in 12 months and the total study duration will be 24 months.

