10.5 SAMPLE SIZE

A sample size of 27 achieves 83.8% power to detect a difference ($P_1 - P_0$) of 0.18 using a one-sided exact test with a target significance level of 0.1000. The actual significance level achieved by this test is 0.0986. These results assume that the population proportion under the null hypothesis (P_0) is 0.15.

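### Appendix 2 counts clear-margin resection of target lesions as a PR with no required shrinkage, and the plan has no ORR analysis that shows whether success depends on it

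*Combined protocol and SAP*

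**What the plan says.** **Appendix 2.** The composite table gives SD when the clinical and radiographic assessments are both SD, and PD when either is PD. The sentence below the table adds a further route to response: "if all previously inoperable target lesions are rendered operable with clear margins obtained at the time of surgery, this will be considered a PR". It sets no shrinkage threshold and asks for no assessment before surgery. It does not define operability, names no one to judge it, and does not say how it ranks against the table's rows.

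**Section 7.4.** "Surgical resection of target lesions is only permissible if all previously identified target lesions are rendered operable". For the effect on response assessment, this section sends the reader to Appendix 2.

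**Section 5.1, criterion 12.** The disease must not be amenable to surgery or radiation. A surgeon's finding that the tumour is unresectable is one listed ground. Another is "surgical morbidity unacceptable by the patients".

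**Section 10.4.2.** The section states: "All response assessments are done by RECIST 1.1 analysis of radiologic scans". It then applies the composite criteria of Appendix 2 in some patients. Patients who cannot be evaluated count as not responding. No analysis separates responses reached through surgery.

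**Section 10.5.** "A sample size of 27 achieves 83.8% power to detect a difference" "of 0.18 using a one-sided exact test with a target significance level of 0.1000", with a null rate of 0.15. "The actual significance level achieved by this test is 0.0986".

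**The concern.** The primary objective is the response rate to cemiplimab, tested in one arm against a fixed 15%. For a patient who would otherwise be scored as a non-responder, the surgical sentence can move the result in one direction only, and there is no control arm in which the same rule would operate.

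Two patients with the same stable measurements can therefore be scored differently because one was operated on with clear margins. Whether that reflects the drug depends on why the lesions came to be regarded as operable. The plan gives no criterion for that change. Sections 7.4 and Appendix 2 rely on the same undefined condition, and criterion 12 uses different language at entry that is not tied to it.

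At stake is the meaning of a positive result. With 27 patients, each such case adds 1/27 = 3.7 percentage points to ORR, and the pass mark is only a few responses above what the null rate predicts.

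**Working it through.** **Inputs from Section 10.5:** n = 27, P0 = 0.15, P1 = 0.15 + 0.18 = 0.33, one-sided exact test, target level 0.10.

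**Input not in the documents:** the number of patients scored PR through surgery who would otherwise be non-responders. It is treated below as an assumption and varied.

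**Step 1. Reproduce the plan's own figures.** Let X be the number of responders, X ~ Bin(27, p).
- P(X ≥ 6 | 0.15) = 0.2097, above 0.10, so 6 is not enough.
- P(X ≥ 7 | 0.15) = 0.0986, which matches the stated actual level.
- P(X ≥ 7 | 0.33) = 0.838, which matches the stated power of 83.8%.

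The test therefore passes at 7 of 27 (25.9%). The expected count under the null is 27 × 0.15 = 4.05.

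**Step 2. A fixed number k of surgical PRs.** Suppose k patients are surgical PRs who would otherwise be non-responders, and the other 27 − k respond at 15%. The chance of passing is P(Y ≥ 7 − k), with Y ~ Bin(27 − k, 0.15).

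| k (assumed) | Chance of passing at a true rate of 15% |
|---|---|
| 0 | 0.0986 |
| 1 | 0.185 |
| 2 | 0.318 |
| 3 | 0.495 |

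**Step 3. A share s of non-responders converted.** This version does not fix the count. The apparent response rate is 0.15 + 0.85s, and the expected number of surgical PRs is 27 × 0.85 × s.

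| s (assumed) | Expected surgical PRs | Apparent rate | Chance of passing |
|---|---|---|---|
| 0% | 0 | 0.150 | 0.0986 |
| 2% | 0.46 | 0.167 | 0.152 |
| 5% | 1.15 | 0.1925 | 0.253 |
| 10% | 2.29 | 0.235 | 0.456 |

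Both versions show that the test is sensitive to one or two reclassified patients. Neither says how many there will be.

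**Step 4. Compare the scoring rules.** Take a patient with clinical SD and radiographic SD. The table scores SD, a non-response. If the lesions are then judged operable and removed with clear margins, the sentence below the table scores PR, a response. No measurement has to differ between the two. For a patient with PD the table scores PD, and the sentence is silent on whether it displaces that.

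**The case against.** The strongest reply is that this is a deliberate response rule, written into the criteria and cross-referenced from Section 7.4. Turning inoperable disease into disease removed with clear margins may be a real benefit of treatment. The rule is also narrow: every target lesion must have been inoperable and become operable, margins must be clear, and Section 7.4 bars other resection of target lesions. Section 10.4.2 uses Appendix 2 only in some patients, and the documents give no expected number of resections, so the inflation could be nil.

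Most of this stands as a limit on scope. It does not supply the missing piece, which is a measured or defined change in the tumour.

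Some stronger readings are tempting but not supported:

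- A reader might infer that surgery makes a responder regardless of how the tumour behaved. The wording requires lesions to be rendered operable, which implies a change on study, although none is measured.
- A reader might infer that a progressing patient can be converted to PR. The table scores PD as PD and the surgical sentence does not claim to override it. Precedence is unstated; conversion is not a stated rule.
- A reader might infer that a patient who simply refused surgery and later accepted it becomes a responder. Criterion 12 speaks of unacceptable surgical morbidity, not refusal for any reason, and nothing equates that ground with being inoperable under Appendix 2. The route is a possible reading of undefined terms.
- A reader might infer that resection lengthens PFS for reasons unrelated to the drug. Section 10.4.3 only summarises PFS by Kaplan-Meier, with no test and no rule for resection. If treatment made surgery possible, the delay is not unrelated to it.

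**Conclusion.** The point holds in a limited form. Under the rule as written, a patient with stable disease on both assessments can count as a responder in the primary ORR after clear-margin resection, with no shrinkage required and no planned analysis that shows the result without such cases. Conversion without tumour change is neither stated nor clearly excluded, because the terms are undefined and do not line up across Section 5.1, Section 7.4 and Appendix 2.

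The size is conditional. At a true rate of 15%, one, two or three surgical PRs who would otherwise be non-responders raise the chance of passing from 9.9% to 18.5%, 31.8% or 49.5%. This assumes those counts, assumes none of those patients would have met PR or CR otherwise, and takes the remaining patients at 15%. It measures the design's sensitivity and does not predict the bias. The change should be made, but the rule need not be removed from the primary definition.

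**What to change.** **Section 10.4.2.** Prespecify that:
- ORR and the exact test are also reported with each surgical PR reclassified to the best composite response recorded before surgery;
- the number of surgical PRs is reported;
- a positive result that depends on them is not attributed to tumour response alone.

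**Appendix 2.** State that a surgical PR does not override a prior PD. Reconcile the term inoperable with criterion 12 in Section 5.1 and with the condition in Section 7.4, so that it is clear which patients the sentence covers. This concerns how outcomes are scored, not who is operated on.

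**Cost.** A few sentences and one extra analysis. The CRF should be checked: Section 7.4 promises recording of local therapies for metastatic lesions, so capture of resection and margin status for locally advanced target lesions needs to be confirmed.

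The sensitivity ORR may be lower than the primary one. Scans on treatment are about 9 weeks apart (Section 4.1), so the last assessment may precede surgery by up to about that long and miss some shrinkage that made surgery possible. The sensitivity figure may therefore err on the low side and should be read beside the primary ORR, not in place of it.
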